(The following paragraph supersedes Clarification Memo [CM] #2, dated 01/02/1014.) Directed biopsies will be obtained from areas suspicious for CIN. ~~Biopsies are taken only if lesions are seen upon colposcopy.~~ In the event lesions are not seen upon colposcopy but the cytology specimens show presence of HSIL, then the participant should return to the study clinic for repeat colposcopy and other diagnostics procedures such as endocervical curettage (ECC), random cervical biopsies (**if not already done**), or diagnostic LEEP. Results of these diagnostic tests must be recorded on the appropriate CRF. ~~Slides from biopsies of CIN2+ and biopsies without CIN2+ will be submitted for review.~~ If CIN2+ is detected by biopsy, the participant will undergo LEEP.

- c. Sample Informed Consent, What do I have to do if I am in this Study?, Groups A and B: At the study visit about 6, 18, and 30 months after the entry visit you will also have a colposcopy and biopsies if any abnormal areas are seen. **At months 18 and 30, you will have two biopsies performed whether or not abnormal areas are seen.**

3. Additional clarifications were made to Section 6.3.10.

- a. The subsection, "Diagnoses," now reads:

Diagnoses

(Per CM #1, dated 02/05/1013.) After entry, record any new diagnoses made since the last visit using the ACTG criteria for clinical events and other diseases.

(Per CM #1, dated 02/05/1013.) Except for invasive cancer, cervical cytology and histology results do not need to be recorded as events; these results will be entered on study-specific CRFs only.

(New language) Record all histology results from procedures for the diagnosis or treatment of cervical HSIL (such as cervical conization or hysterectomy) and from biopsies performed related to the presence or absence of squamous intraepithelial lesions on the appropriate CRFs.

- b. The subsection, "LEEP," now reads:

(The following paragraph supersedes item 4b in LoA #2, dated 08/09/1012.)

LEEP

Participants found to have CIN2+ by biopsy at any point during the study will be offered LEEP **or other excisional treatment** (except for participants in Arm A **prior to week 26** who have CIN2+ on pre-cryotherapy biopsy at entry). If the participant had a prior LEEP, treatment of recurrent **or incompletely treated**

CIN2+ is at the discretion of the site investigator. These participants will continue on study.

(No changes to the remainder of this subsection.)

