The Arm A box now reads: **Cervical biopsies + Immediate cryotherapy (N=140)**

2. Section 1.3, Secondary Objectives

- 1.3.6 To evaluate baseline/screening characteristics (detection of various HPV types, CD4, CD4 nadir, HIV RNA, **sexual history, and recent sexual activity**) associated with cytological abnormalities at baseline.
- 1.3.8 To report the proportion of HIV-infected women with extensive cervical lesions inappropriate for cryotherapy and examine possible factors associated with these lesions, including CD4 count, plasma HIV-1 RNA, ART use, HPV types detected, **sexual history, and recent sexual activity**.

3. Section 2.2, Rationale, PEPFAR Objectives

The PEPFAR objectives in section 1.3.5 will use screening and baseline evaluations from all women who give consent for this study.

4. Section 3.0, Study Design, 4th Paragraph

All participants in Arm A (HPV test-and-treat) will undergo one or two cervical biopsies followed by immediate cervical cryotherapy at entry. Up to two visible lesions should be biopsied. If no lesions are seen, then one normal-appearing area of the cervix should be biopsied at a location of the investigator's choosing to ensure that at least one biopsy is collected. Participants in Arm A will receive the results of the cytology, but participants will receive cryotherapy treatment regardless of the results.

5. Section 4.1.3

For candidates suitable for cervical cryotherapy (as defined in section 4.1.5 below), hr-HPV detected by aHPV within 30 days prior to study entry.

6. Section 5.1.1, Cervical Cryotherapy

One or two cervical biopsies will be performed. This will be followed by cervical cryotherapy: Two 3-minute freezes separated by 5 minutes of thawing. Refer to the A5282 MOPS for a detailed description of this procedure.

7. Section 6.1, Schedule of Events

The row "Cryotherapy (Arm A only)" now reads "**Cervical biopsies/cryotherapy (Arm A only).**"

8. Section 6.3.10, Other Laboratory Studies and Procedures

Colposcopy and Directed Biopsies

At entry:

- Participants in Arm A will ~~not have colposcopy and directed biopsies; these women will instead undergo have one or two cervical biopsies performed followed by immediate cervical cryotherapy.~~

LEEP

All specimens obtained by LEEP will be fixed in formalin and submitted for **local** review.

Cryotherapy (Arm A Only)

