Participants in Arm A will undergo cervical cryotherapy within 7 days after entry. **Please see the A5282 MOPS for details. All women in Arm A should undergo one or two cervical biopsies immediately prior to cervical cryotherapy. Up to two visible lesions should be biopsied. If no lesions are seen, then one normal-appearing area of the cervix should be biopsied at a location of the investigator's choosing. At least one biopsy is collected.** Digital images obtained immediately prior to and following cryotherapy will be submitted for review.

9. Section 7.3, Other Diseases/Conditions, Invasive Cervical, Vaginal, or Vulvar Cancer, Last Paragraph

Participants who are diagnosed with cervical, vaginal, or vulvar cancer after enrolling into the study will continue to be followed on study. These participants will come into the clinic per the time points in Section 6.1 for study evaluations. These participants will receive additional treatments as indicated in the site-specific clinical management plan. **Any women in Arm A diagnosed with invasive cervical cancer on the biopsies obtained immediately prior to cryotherapy should be seen as soon as possible for evaluation by a local specialist and treated as per standard of care in that country.**

10. Section 9.2.2, Secondary Endpoints

9.2.2.11 Sexual history at baseline (age at first vaginal sex and lifetime number of vaginal sex partners) and recent sexual activity (number of vaginal sex partners and condom use within the previous 6 months).

11. Section 9.6, Analyses

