Johannesburg, South Africa. [name] and colleagues of the University of Witwatersrand recently published data on the prevalence of HPV infections and cervical squamous intraepithelial lesions (SIL) on cytology in HIV-infected women in Johannesburg, South Africa recruited from the government outpatient HIV clinic [30]. One thousand and ten HIV-infected women with a median age of 34 and CD4 count of 231 cells/ μ L were screened with cervical cytology and a subset screened with HPV DNA PCR. Five hundred and three (50%) of these women had an abnormal cervical cytology: 84 (8%) had atypical squamous cells, 237 (23%) low-grade lesions and 182 (18%) had high grade lesions. Among the 191 women with HPV DNA PCR results, 138 (72%) had one or more types of hr-HPV detected by PCR and 51% had more than one hr-HPV type detected. Among 90 women with normal cytology, 54 (60%) had one or more types of hr-HPV detected. HPV 16 was detected in 42% of women with HSIL and HPV 18 in 3%. High risk-HPV by DNA PCR was related to current CD4 count: 72 (82%) of women with a CD4 <200 cells/mm³ had hr-HPV by PCR compared with 7 (41%) of women with a CD4 >500 cells/mm³.

Pune, India. Investigators have shown that in a cross-sectional assessment of 303 HIV-infected women, 83 (27.7%) had colposcopic-histopathological evidence of CIN1+ lesions and 50 (16.5%) had evidence of advanced CIN2+ neoplastic disease [31]. High risk-HPV by Digene HC2 was detected in 41.7% (124/297) of participants. On multivariable ordinal logistic regression, the independent predictors of increasing severity of CIN included (i) receiving ART [adjusted odds ratio (aOR): 2.16 (1.15, 4.04), p=0.02] and (ii) being hr-HPV positive [aOR: 1.91 (1.12, 3.26), p=0.02].

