6.3.10 Other Laboratory Studies and Procedures

Refer to the A5282 MOPS for detailed instructions on how to perform colposcopy and biopsies, collect specimens for aHPV, HPV DNA PCR, and *careHPV*, perform cervical cytology, cryotherapy, and LEEP, and detailed plans for the quality assurance of clinical procedures.

Participants must refrain from any kind of sexual activity, douching, and inserting any intravaginal products for at least 48 hours prior to the collection of vaginal/cervical specimens.

Speculum Examination and Colposcopy

Participants will undergo a speculum examination at screening to obtain cervical specimens for HPV testing and cytology. If participants have visual evidence of bacterial STIs or an examination consistent with pelvic inflammatory disease, then samples for HPV testing and cytology should not be obtained. Instead, these women should be treated according to the local standard of care, in which case screening evaluations can be performed a minimum of 7 days after initiating treatment.

A trained examiner will also perform colposcopy at screening to determine whether the participant's cervix is suitable for cryotherapy and for visual impression only. Digital images will be taken using a video colposcope provided to sites by the study, and submitted for review along with the colposcopic impression provided by the examiner as to the degree of CIN (no lesions seen, lesions seen appropriate for cryotherapy, lesions seen not appropriate for cryotherapy). Refer to the A5282 MOPS for detailed procedures.

No biopsies are to be obtained at screening unless the examiner is suspicious of invasive cervical, vaginal, or vulvar cancer, in which case the participant will not be enrolled into the study and will be managed as per section 7.3.

aHPV

A cervical specimen will be obtained at screening for real-time aHPV testing. Post-entry, specimens will be obtained for aHPV and stored locally (refer to the A5282 MOPS).

HPV DNA PCR

Specimens will be stored for HPV DNA PCR. Testing will be performed on the same specimen as the aHPV. Specimens may be shipped to the U.S. for HPV typing at a central laboratory, if permitted by in-country regulations, or batch tested at a local or regional laboratory. Specimens obtained by LEEP will also be stored locally for possible future testing by HPV DNA PCR.

careHPV

A cervical cytobrush specimen will be obtained for *careHPV* and stored locally in the appropriate media (refer to the A5282 MOPS).

Cytology

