Cervical cytology specimens will be obtained and processed locally in real-time (refer to the A5282 MOPS). Pap smears will be interpreted locally. Results should be communicated to the participant's primary care provider, and the site must document this communication in the source documents.

Colposcopy and Directed Biopsies

At entry:

- Participants in Arm A will not have colposcopy and directed biopsies; these women will instead undergo cryotherapy.
- Participants in Arm B will undergo colposcopy with directed biopsies if the screening cytology is abnormal, i.e., the result reveals atypical squamous cells of undetermined significance (ASCUS), atypical glandular cells of undetermined significance (AGUS), low grade squamous intraepithelial lesion (LSIL), or HSIL.
- Participants in Arm C will undergo colposcopy and directed biopsies if the screening cytology shows HSIL or if cervical lesions were seen upon visual inspection.

Post entry:

- Participants in Arms A and B will undergo colposcopy and directed biopsies at the weeks 26, 78, and 130 clinic visits.
- Participants in Arm C who undergo LEEP post-entry will undergo colposcopy and directed biopsies at the week 26 clinic visit.

Digital images and colposcopic impression will be submitted for review, along with location of cervical biopsies.

Directed biopsies will be obtained from areas suspicious for CIN. Biopsies are taken only if lesions are seen upon colposcopy. In the event lesions are not seen upon colposcopy but the cytology specimens show presence of HSIL, then the participant should return to the study clinic for endocervical curettage (ECC). Slides from biopsies of CIN2+ and biopsies without CIN2+ will be submitted for review. If CIN2+ is detected by biopsy, the participant will undergo LEEP.

LEEP

Participants found to have CIN2+ by biopsy at any point during the study will be offered LEEP. If the participant had a prior LEEP, treatment of recurrent CIN2+ is at the discretion of the site investigator. These participants will continue on study. All specimens obtained by LEEP will be fixed in formalin and submitted for review. Digital images obtained immediately prior to and following LEEP will also be submitted for review.

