### **3 Statistical Considerations**

Unless otherwise indicated, analysis will use data from all subjects who enrolled successfully to A5282 arms A and B.

For categorical measures, number of subjects and percent will be provided. For continuous measures, median, lower and upper quartiles, minimum and maximum will be provided. In data listings, participants will be identified by an anonymous patient identifier generated at the statistical center. Dates will not be shown, but will be converted to time (e.g. weeks) since randomization.

Time to CIN2+ will be computed as the number of weeks between randomization and the week 26 to week 130 biopsy week when CIN2+ was first detected. For those who did not develop CIN2+, event time will be censored at the latest among the following: time of last biopsy or last colposcopy or last pap smear. The cumulative rate of CIN2+ will be estimated using Kaplan-Meier methods. A one-sided 95% upper confidence bound on Arm B minus Arm A cumulative rates accounting for baseline ART use (i.e. [using inverse variance as weights,] weighted estimate of treatment difference across baseline ART use) will be provided.

The per-protocol secondary analysis of the primary endpoint will only include:

- a. Arm A participants who had week 0 cryotherapy, and
- b. Arm B participants with: 1) baseline NILM cytology, 2) baseline abnormal cytology (ASCUS or greater) with one or more cervical biopsies that show NILM or CIN1 as the most severe result, 3) baseline abnormal cytology (ASCUS or greater) who underwent cervical colposcopy with no lesions seen, or 4) women who had LEEP performed prior to week 16 after the week 0 CIN2+ on biopsy regardless of cytology result.

All programs that generate derived data will be validated. The calculations of time to CIN2+ and confidence interval for the primary endpoint (one-sided 95% upper confidence interval for arm B proportion minus arm A proportion) will be double-programmed.

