Figures (ITT): survival curves with p-value from stratified log-rank test comparing arms A and B for those with: (a) CIN2+ on histology at baseline, (b) CIN1 on histology at baseline, (c) NILM cytology result at baseline, (d) ASCUS/LSIL cytology result at baseline and (e) HSIL/ASC-H cytology result at baseline.

**4.2.2 Secondary endpoint:** CIN3+ (CIN3 or invasive cancer) by biopsy 26 weeks post randomization through 130 weeks post randomization, as determined by local review at a DAIDS-assessed laboratory.

NOTE: Time to CIN3+ will be computed as the number of weeks between randomization and the biopsy week when CIN3+ was detected. For those who did not develop CIN3+, event time will be censored at the latest among the following: time of last biopsy or last colposcopy or last pap smear.

Tables (ITT and per-protocol): cumulative rates of arm A and arm B subjects who developed CIN3+ from week 26 to week 130; two-sided 95% CI for arm B proportion minus arm A proportion.

Figures: survival curves with p-value from stratified log-rank test comparing arms A and B

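### SAP 4.2.1 tests Arm A against Arm B within baseline-histology CIN2+ and CIN1, but entry histology is obtained after randomization under different rules in each arm

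*SAP*

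**What the plan says.** SAP 4.2.1 lists ITT survival curves, each with a stratified log-rank p-value for Arm A against Arm B, in five baseline subgroups. Two are defined by histology: "a) CIN2+ on histology at baseline, (b) CIN1 on histology at baseline". The other three, (c) to (e), are defined by cytology. The SAP does not define baseline histology. It does not mark these figures as exploratory, although it uses that label in 4.2.5 and 4.2.7.

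The protocol determines when and in whom entry histology exists:

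- **Screening, all women (Protocol 6.3.10):** "No biopsies are to be obtained at screening unless the examiner is suspicious of invasive cervical, vaginal, or vulvar cancer". Women with such suspicion are not enrolled.
- **Arm A at entry (Letter of Amendment #1, revised Sections 3.0 and 6.3.10):** "All women in Arm A should undergo one or two cervical biopsies immediately prior to cervical cryotherapy". Up to two visible lesions are sampled, and "If no lesions are seen, then one normal-appearing area of the cervix should be biopsied".
- **Arm B at entry (Protocol 6.3.10):** "Participants in Arm B will undergo colposcopy with directed biopsies if the screening cytology is abnormal". Directed biopsies come from areas suspicious for CIN. A further work-up applies "In the event lesions are not seen upon colposcopy but the cytology specimens show presence of HSIL" (Clarification Memo #2, retained in the Letter of Amendment that follows the March 2015 DSMB review).

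The per-protocol definition in SAP 3 fits this reading. It counts as adherent Arm B women with normal cytology, and those with "baseline abnormal cytology (ASCUS or greater) who underwent cervical colposcopy with no lesions seen", without requiring a biopsy.

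**The concern.** A subgroup comparison keeps the protection of randomization if membership is fixed before assignment, or at least measured in the same way in both arms. Neither holds for panels (a) and (b). Entry biopsies precede cryotherapy or LEEP, so treatment does not alter the histology. The problem is ascertainment: who is biopsied depends on the assigned arm.

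Panel (a) is the one most likely to be over-read. After an entry finding of CIN2+, Arm A women have had cryotherapy and Arm B women are offered LEEP. A p-value under an ITT label would look like a randomized comparison of those two courses in women with proven disease. A difference could instead arise because the Arm A panel includes cytology-negative disease and the Arm B panel does not.

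**Working it through.** **The plan's own figures.** Protocol 9.4 takes 24% of hr-HPV-positive women to have CIN2+ at first colposcopy, cytology sensitivity of about 80% and treatment efficacy of 90%. The product is 0.24 × 0.80 × 0.90 = 17.3%, which matches the stated 17%. The 111 evaluable women per arm also reproduce (20% against 6%, one-sided 5%, 90% power, continuity-corrected). With 20% loss, 111/0.80 = 139, against 140 stated. None of these figures is disputed. The plan gives no figure for the histology panels.

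**Who can be classified.** In the Johannesburg data (Protocol 2.1), 138 of 191 women with PCR results had hr-HPV, and "Among 90 women with normal cytology, 54 (60%) had one or more types of hr-HPV detected". Taking those 90 to be among the 191, 54/138 = 39% of hr-HPV-positive women had normal cytology (Wilson 95% CI 31-47%). If that held here, 0.391 × 140 ≈ 55 Arm B women would have no protocol entry biopsy, against none in Arm A. This is one site, with HPV by PCR and no selection for cryotherapy suitability. It shows how many women the rule affects, not the size of the bias.

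**Expected size of panel (a).** Assume 140 per arm, 24% CIN2+, fully sensitive biopsy, and cytology sensitivity *s* of 80% (Protocol 9.4) or 70% (from the 30% false-negative rate in Protocol 2.1).

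- Arm A: 0.24 × 140 = 33.6.
- Arm B: 0.24 × *s* × 140 = 26.9 (80%) or 23.5 (70%).
- Arm A women with no Arm B counterpart: 6.7 (20% of the Arm A panel) or 10.1 (30%).

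**Spurious difference with no arm effect.** Let r1 be the later CIN2+ risk in cytology-abnormal women and r2 the risk in cytology-normal women. The Arm B panel has risk r1 and the Arm A panel *s*·r1 + (1 − *s*)·r2. Hence B − A = (1 − *s*)(r1 − r2), which is zero only if r1 = r2. Lower risk in cytology-normal women favors Arm A; higher risk favors Arm B. The documents give neither risk.

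**Type I error, by simulation.** 10,000 trials per scenario, 140 per arm, log-rank test stratified by ART (50/50), events spread equally over weeks 26, 78 and 130, 20% dropout, no arm effect, two-sided 5% test (the level in Protocol 9.6.2). Risks are assumed.

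| r1 / r2 (%) | Error, *s* = 80% | B − A (points) | Error, *s* = 70% | B − A (points) |
|---|---|---|---|---|
| 30 / 30 | 4.9% | 0 | 4.7% | 0 |
| 30 / 15 | 5.8% | 3 | 7.3% | 4.5 |
| 30 / 5 | 7.1% | 5 | 9.6% | 7.5 |
| 50 / 50 | 5.0% | 0 | 4.9% | 0 |
| 50 / 25 | 6.6% | 5 | 8.4% | 7.5 |
| 50 / 10 | 8.8% | 8 | 13.3% | 12 |

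A repeat of five of these scenarios in separate code (4,000 trials each) agreed within about 0.6 points.

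**Panel (b).** The documents give no CIN1 prevalence, so it cannot be sized. The same selection applies.

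**A possible second asymmetry.** SAP 4.2 treats LEEP results before week 16 as baseline evaluation. Letter of Amendment #2 exempts Arm A women with CIN2+ on the pre-cryotherapy biopsy from the offer of LEEP; the later Letter limits that exemption to the period before week 26. If LEEP histology feeds the undefined baseline histology, it could reclassify Arm B women with entry CIN2+ but not their Arm A counterparts.

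**The case against.** The case on the other side accepts that panels (a) and (b) are not protected by randomization. It argues that the harm is small and partly guarded against.

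- **General caveat.** Protocol 9.6.2 says the study is not powered to test secondary objectives formally and makes no multiplicity adjustment. That limits the weight of these p-values, but it does not remove selection bias.
- **Per-protocol item 4.** SAP 3 also admits Arm B women who had early LEEP after week 0 CIN2+, whatever their cytology. So that definition does not by itself prove an absolute exclusion. The biopsy rule in Protocol 6.3.10 still does so by protocol.
- **Assumed risks are high.** This stands. Whole-arm design rates are 6% and 20%, and treatment is assumed 90% effective. At r1 = 20% and r2 = 5-10%, simulated error is 5.8-7.2% with a difference of 2-4.5 points. At r1 = 10% and r2 = 0-5%, it is 4.0-6.6% with 1-3 points.
- **Opposite direction.** With r1 = 15% and r2 = 30%, error is about 5-6%.
- **Fully sensitive biopsy.** This also stands. If Arm A's one or two biopsies find 50-75% of lesions, panel (a) has 16.8-25.2 Arm A women, and the size imbalance can vanish or reverse. At 60% yield most tabulated scenarios fall to about 4.6-7.5%, and the most extreme to 11%.
- **Existing listings.** SAP 4.1.4 lists Arm B women with abnormal cytology and no baseline biopsy, and SAP 4.2 reports baseline CIN2+. Neither shows the cytology-normal Arm B women who were not biopsied.

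These points reduce the likely size of the bias. They do not make the comparison randomized.

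**Conclusion.** The concern holds. Membership of panels (a) and (b) depends on the assigned arm, so an ITT label and a between-arm p-value are not justified there. This follows from the biopsy rules and needs no numerical assumption.

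The size is uncertain. Under the tabulated unequal-risk assumptions with fully sensitive biopsy, two-sided type I error in panel (a) is about 6-9% at 80% cytology sensitivity and 7-13% at 70%. At later risks of 10-20% it is about 4.5-7%, and with equal risks it stays near 5%. Lower biopsy yield in Arm A generally reduces the inflation. The direction cannot be known from the documents, so a reader could not correct for it.

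The whole-arm primary comparison is not touched by this point. Nor are panels (c) to (e), which rest on cytology taken in all women before randomization. The change should be made, but it does not threaten the trial's main conclusion.

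**What to change.** In SAP 4.2.1:

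1. Show panels (a) and (b) descriptively by arm, with no between-arm p-value and no ITT label.
2. Place beside them a table of the number biopsied at entry, by arm and screening cytology.
3. Base between-arm subgroup comparisons on the cytology panels (c) to (e).
4. Define baseline histology by specimen and time window, as the entry punch biopsy, so that LEEP results before week 16 do not enter it.

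If a histology comparison is kept, restrict both arms to women with abnormal screening cytology and a visible lesion at screening colposcopy, both recorded before randomization. Label it exploratory. State that sampling still differs: up to two lesions in Arm A, no stated cap in Arm B. This is only a partial repair.

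The cost is SAP wording; the data are already collected. Two secondary p-values are lost or, under the restricted version, the CIN2+ panel shrinks to fewer than about 27 women per arm on the illustration above.
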